When a patient fails to respond to a benzodiazepine and the initial second-line IV AED, they are classified as having refractory SE (RSE). Refractory SE develops in 31% to 50% of patients with SE and has a mortality of 16 to 39%.^{1,10,11} Because SE tends to become more refractory as it progresses, patients who fail second-line IV AEDs may require treatment with an IV anesthetic.^{12,13} Third-line agents such as pentobarbital, midazolam and propofol are administered at anesthetic doses to induce coma that is maintained for 24 hours or longer, after which the dose of anesthetic agent is reduced to determine whether seizure activity has been aborted. IV anesthesia is an independent risk factor for increased morbidity and mortality in SE, with longer duration of anesthesia associated with a worse prognosis.^{14,15,16}

Few drugs are approved for the treatment of SE and there is a need for more evidence-based, efficacious therapies. Treatment resistance in SE has been partially attributed to the internalization of post-synaptic γ -aminobutyric acid (GABA)_A receptors and externalization of glutamate receptors.^{10,12} With the down-regulation of GABA_A-mediated synaptic inhibition that occurs in SE, antiepileptic treatments relying on enhancement of synaptic GABA_A neurotransmission become less effective.

Ganaxolone is a potent positive allosteric modulator of GABA_A receptors that binds at a site distinct from that responsible for the action of benzodiazepines and barbiturates.¹⁷ Unlike benzodiazepines, neuroactive steroids such as ganaxolone bind to both synaptic and extrasynaptic GABA_A receptors.¹⁸ By enhancing GABA_A receptor function, especially through its action at extrasynaptic GABA_A receptors, ganaxolone provides an alternative mechanism in the treatment of seizures. Thus, ganaxolone may serve as a novel and effective therapy in the management of SE.

The ganaxolone to be used for this study is a proprietary IV formulation solubilized by Captisol® (betadex sulfobutyl ether sodium). Dosing targets plasma concentrations of ganaxolone that mimic those associated with anticonvulsant effects in preclinical animal models of SE and that are expected to demonstrate anticonvulsant properties in humans. The dose of Captisol® will not exceed 50 g/day (1.25 g/kg/day in participants weighing <40 kg) which corresponds to a maximum ganaxolone dose of 833 mg/day (20.825 mg/kg/day in participants weighing <40 kg).

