The ganaxolone IV to be used in this study is a proprietary formulation that is solubilized with Captisol® (betadex sulfobutyl ether sodium), with the dose of Captisol® not exceeding 50 grams per day.

Among the 17 enrolled subjects who received GNX, the most common TEAE were somnolence (5 subjects, 29.4%), hypotension (4 subjects, 23.5%), and hypokalemia (3 subjects, 17.6%). Severe TEAEs were reported in 6 subjects (35.3%). The most frequently (reported in 2 or more subjects [i.e., $\geq 10\%$]) reported severe TEAEs by system organ class were Nervous System Disorders, reported in 4 subjects (23.5%). Refer to the GNX IB for detailed safety information.

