5.2.2 Prohibited Treatment

If a participant progresses at any time during the study to an IV anesthetic (e.g., midazolam, propofol, thiopental, or pentobarbital) given with the primary intent specifically to treat seizures or achieve burst suppression IP administration will be discontinued without taper but the participant will continue in the study. Additional details can be found in [Section 4.5](#).

Concomitant use of IV products containing Captisol® during IP administration is prohibited (see exclusion criterion #7 and Appendix 4).

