7.1.3 Follow-up Period (starting at IP discontinuation through Week 4)

Participants will have the follow-up period assessments/procedures collected following IP discontinuation (with or without taper) as noted in [Section 3](#). Assessments/procedures will be collected every 24 hours through 120 hours (or until hospital discharge) and at the time of hospital discharge, followed by weekly follow-up visits/contacts at Week 1, 2, 3 and 4.

Participants who discontinue IP without a taper, e.g., were administered IP for less than 2 hours, progress to anesthesia for seizure suppression or discontinue IP due to safety or any other reason, except due to withdrawal of consent, will have the follow-up assessments/procedures collected every 24 hours through 120 hours (or until hospital discharge) and at the time of hospital discharge, followed by weekly follow-up visits/contacts at Week 1, 2, 3 and 4.

The follow-up period for this protocol is approximately 4 weeks. Week 1, 2, 3, and 4 visits may be conducted as an inpatient visit, if the participant is still in the hospital, or as a telephone contact, if the participant has been discharged. Attempts should be made to have discharged participants return for one of these visits to be in person. The participant/participant's parent/guardian/LAR, as appropriate, will receive a follow-up contact weekly approximately 7 ± 3 , 14 ± 3 , 21 ± 3 , and 28 ± 3 days following the IP discontinuation date. If the hospital discharge visit corresponds to the Week 1, 2, 3, or 4 (± 3 days) visits, it can take the place of the weekly visit.

During these follow-up period visits/contacts, the site will follow-up on all SAEs and non-serious AEs, AE resolution that occurs, and concomitant medications. Adverse events and SAEs that are not resolved at the time of contact will be followed to closure (see [Section 8.1](#)). [Table 1](#) lists the assessments that should be collected during the follow-up visits/contacts.

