7.2.3.3 Adverse Event Collection

Participants and their parent/guardian/LAR will be questioned in a general way to ascertain if AEs have occurred (e.g., “Have you had any health problems since your last visit?”). Adverse events will be collected from the time of IP initiation through the final study follow-up visit/contact.

Refer to [Section 8](#), Adverse and Serious Adverse Events Assessment.

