3.1.6 Investigational Product Infusion Summary

Investigational product will be administered as a 48-hour continuous infusion, which includes an initial 3-minute bolus and ends with a 12-hour taper based on [Table 4](#) and [Table 5](#). The total administered dose (mg) for IP infusion and duration of IP infusion will be summarized based on the Safety Population.

Table 4. Dosing for Participants ≥ 40 kg (on a mg/hour basis)

Days	Start Time from IP Initiation	IP Dose	IP Infusion Rate (mL/hour)	Duration
Day 1	0 hours: bolus dose via syringe or infusion pump	30 mg ^a	N/A	3 minutes (0.05 hours)
Day 1	0 hours through 2 hours following IP initiation: continuous infusion, started with bolus	80 mg/hr	80	2 hours
Day 1	2 hours through 12 hours following IP initiation	40 mg/hr	40	10 hours
Day 1	12 hours through 24 hours following IP initiation	20 mg/hr	20	12 hours
Day 2 ^b	24 hours through 36 hours following IP initiation	20 - 45 mg/hr	20 - 45	12 hours
	Taper			
Day 2 ^c	36 through 48 hours following IP initiation (12-hour taper)	13 - 30 mg/hr	13 - 30	4 hours
		9 - 20 mg/hr	9 - 20	4 hours
		6 - 13 mg/hr	6 - 13	4 hours

IP = investigational product.

- a. The 30 mg bolus is administered over ~3 minutes.
- b. On Day 2 (24 through 36 hours), the continuous infusion rate can be increased from 20 mg/hour to a maximum rate of 45 mg/hour at any time, if needed, to manage seizure relapse or other medical reason.
- c. To taper the IP, the infusion rate at the 36-hour following IP initiation timepoint will be reduced by 33.3% every 4 hours until the infusion rate is stopped or if the infusion rate becomes too low to sustain the infusion line, at which point it will be stopped. The first taper will be 33.3% from the current infusion rate (e.g., if the current infusion rate is 20 mg/hr, the first taper will be 13 mg/hr) the second taper will be 33.3% from the first tapered infusion rate (e.g., if the current infusion rate is 20 mg/hr, the second taper will be 9 mg/hr), and the final taper will be 33.3% from the previous tapered infusion rate (e.g., if the current infusion rate is 20 mg/hr, the final taper will be 6 mg/hr). If, in the investigator's judgment, the taper needs to start at an earlier timepoint during the treatment period, the infusion rate at the start of the first taper will be decreased by 33.3% every 4 hours as described.

Table 5. Dosing for Participants < 40 kg (on a mg/kg/hour basis)

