3.3.1 Adverse Events

Adverse events (AEs) will be coded by MedDRA® version 22.0 or higher and grouped by SOC and PT. The verbatim term will be included in the AE listings. Except where indicated, the summary tables will include only TEAEs. All AEs, treatment-emergent or otherwise, will be presented in participant data listings.

A treatment-emergent adverse event (TEAE) is defined as an AE that occurred or worsened at the time of or following IP initiation. To allow differentiation between the study period in which an AE occurred, two categories are defined based upon onset date. Adverse events that had onset dates prior to the IP initiation are considered "prior." Adverse events with onset dates on or after IP initiation and up to the end of the follow-up period are considered "on-therapy" or equivalently "treatment emergent". Adverse events with onset dates prior to the IP initiation but that worsen after IP starts will be considered treatment emergent.

An overview table, including number and percentage of participants with AEs, TEAEs, TEAEs by highest severity, serious TEAEs, study drug related TEAEs, TEAEs leading to IP discontinuation, and TEAEs leading to death will be provided.

In addition, the following summary tables will be provided:

- TEAE by SOC and PT
- TEAEs by PT
- TEAE by SOC, PT, and severity
- Study drug related TEAE by SOC and PT
- Serious TEAE by SOC and PT
- Serious and drug-related TEAE by SOC and PT
- TEAEs leading to study drug discontinuation by SOC and PT
- TEAEs leading to withdrawal

All AE tables will be sorted by SOC and PT in decreasing frequency of the number of participants in the GNX-treated group. If frequency ties, the sorting will be alphabetic.

A participant having the same AE more than once will be counted only once in the number and percentage of participants' calculation for that AE. Similarly, if a participant had more than one AE in a SOC, the participant will be counted only once in the number of participants with an AE for that SOC. If a participant has the same AE on multiple occasions, the highest severity (severe > moderate > mild) recorded for the event will be presented in the AEs by severity table.

Adverse event listing will be provided for all TEAE, serious TEAEs, TEAE related to IP, TEAE leading to study drug discontinuation, AEs leading to withdrawal, and participants who died during the study.

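### All adverse events over about four weeks are labelled 'on-therapy', and no adverse-event table is split by onset period, so direct drug harm is read together with later harm, including that of IV anesthesia

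*SAP*

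**What the plan says.** SAP 3.3.1 sets out to distinguish the study period in which an event occurred, and says that "two categories are defined based upon onset date". Events that start before investigational product (IP) are *prior*. For the rest, "Adverse events with onset dates on or after IP initiation and up to the end of the follow-up period are considered" *on-therapy*, which the SAP equates with treatment emergent. Every summary table listed there uses this single window, and a participant counts once per event term.

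Four other statements bear on how to read that window:

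- Protocol 7.2.3.3: "Adverse events will be collected from the time of IP initiation through the final study follow-up visit/contact".
- SAP 3.1.6: "Investigational product will be administered as a 48-hour continuous infusion", which includes the 12-hour taper.
- Protocol 7.1.3: "The follow-up period for this protocol is approximately 4 weeks", counted from IP discontinuation.
- Protocol 5.2.2, on progression to an IV anesthetic given to treat seizures: "IP administration will be discontinued without taper but the participant will continue in the study".

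**The concern.** Adverse events are collected only from IP initiation, so the *prior* category is nearly empty and the two-category split separates almost nothing. A participant with hypotension in the first hour of ganaxolone and one with hypotension on day 5 under anesthesia after failing placebo make the same entry in the same row.

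This matters because the trial expects anesthesia use to differ by arm; that is its second co-primary endpoint. The Rationale in the protocol synopsis says that "IV anesthesia is an independent risk factor for increased morbidity and mortality in SE". The harms can overlap. In the phase 2 study (Protocol 2.1) the commonest events on ganaxolone were somnolence (5 of 17) and hypotension (4 of 17). The synopsis also says that benzodiazepines may cause respiratory depression and hypotension, and midazolam is one of the named anesthetics. Safety is part of the primary objective (Protocol 2.2.1). If ganaxolone spares anesthesia, a reader who takes the *on-therapy* table as the drug's own harm profile could miss an acute harm.

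**Working it through.** **The plan's own figure.** No figure is stated for the adverse-event analysis. The relevant one is the power statement in Protocol 10.2, because it fixes the assumed anesthesia rates: response of 75% vs 45%, 62 per arm, two-sided 5%, at least 90% power. With pooled variance under the null:

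- Null SE = √(2 × 0.60 × 0.40 / 62) = 0.0880. Alternative SE = √((0.75 × 0.25 + 0.45 × 0.55) / 62) = 0.0838.
- z = (0.30 − 1.96 × 0.0880) / 0.0838 = 1.52, so power is 93.6% (91.4% by exact Fisher calculation).

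The figure reproduces. For the second co-primary endpoint it implies anesthesia by 36 hours in 25% on ganaxolone and 55% on placebo.

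**Share of the window on drug.** 48 h / (48 h + 28 ± 3 days) = 2/33 to 2/27 = 6.1% to 7.4%. This shows that the label does not fit. It is a share of calendar time, not of events.

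**How far anesthesia could offset a direct excess.** Let *b* be background risk, *g* the direct ganaxolone risk and *r* the risk caused by anesthesia in those who receive it, all independent:

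- Ganaxolone = 1 − (1 − b)(1 − g)(1 − 0.25r)
- Placebo = 1 − (1 − b)(1 − 0.55r)

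The documents give no *b* or *r*. Assume b = 10% and g = 15%. Without anesthesia effects, ganaxolone has 1 − 0.90 × 0.85 = 23.5%, the phase 2 hypotension rate, against 10% on placebo: an excess of 13.5 points.

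| r (assumed) | Ganaxolone | Placebo | Difference shown |
|---|---|---|---|
| 30% | 29.2% | 24.9% | +4.4 |
| 50% | 33.1% | 34.8% | −1.7 |
| 70% | 36.9% | 44.7% | −7.8 |

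(Differences are taken before rounding.)

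**Break-even.** The arms look equal when g = 1 − (1 − 0.55r)/(1 − 0.25r); *b* drops out. The direct risk fully hidden depends on *r* and on the anesthesia gap:

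| r (assumed) | 25% vs 55% | 40% vs 55% |
|---|---|---|
| 0.2 | 6.3 points | 3.3 points |
| 0.4 | 13.3 points | 7.1 points |
| 0.6 | 21.2 points | 11.8 points |
| 0.8 | 30.0 points | 17.6 points |

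With equal anesthesia use nothing is hidden. At g = 15% the sign reverses only if r exceeds 0.15/0.3375 = 44%.

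**Where the offset arises.** The 25% and 55% are 36-hour rates, inside the planned 48-hour infusion. A fixed 48- or 72-hour calendar window would therefore mix the same events. What separates them is the actual IP stop, which Protocol 5.2.2 ties to the start of anesthesia.

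**The case against.** The strongest reply is that nothing is biased. IP is added to standard of care, and anesthesia after failure is part of that care. The whole-period table compares randomized strategies intact, and fewer harms from spared anesthesia would be a real benefit. This stands. A reader might infer that the planned safety comparison is invalid; the documents do not support that. The weakness lies in the label and in the absence of a second view.

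Three further stronger readings also fail:

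- *That the four-week length causes the offset.* It does not, as the 36-hour rates show.
- *That 'on-therapy' should be redefined to end at anesthesia.* That cut depends on outcome. Under the trial's hypothesis it truncates placebo participants more often, which lowers their event percentages and tilts the table against ganaxolone.
- *That acute harm would go unseen.* Blood pressure and oxygen saturation are summarized by time point (SAP 3.3.2), sedation by visit (SAP 3.2.3.7), and ventilation started during infusion by arm (SAP 3.2.4.2). Tables of drug-related TEAEs and of those leading to drug discontinuation are planned too.

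These outputs help but do not replace a TEAE table by period. They cover a few effects, or rest on investigator attribution under guidance that excludes events explained by other therapies (Protocol 8.1.2), or capture only events that stopped the drug.

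The inputs are also soft. The 4 of 17 comes from an uncontrolled study (exact 95% interval about 7% to 50%). At its upper end ganaxolone stays 14 to 29 points worse in all three scenarios. With about 50 per arm, a 13.5-point excess has a 95% interval of about −1 to +28 even with no anesthesia effect.

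**Conclusion.** The point holds as one of labelling and missing description. The single *on-therapy* window does not match a 48-hour infusion, and no planned adverse-event table allows events during infusion to be read apart from later ones. Offset of a direct harm is possible, not predicted. It requires that ganaxolone reduces anesthesia use and that the same event term arises from both exposures. Under the planning rates it could hide a direct risk of about 6 to 30 points for *r* between 0.2 and 0.8. That range is illustrative: *r* and *b* are assumptions, and 25% vs 55% are design values at 36 hours, not results or four-week rates. Some extension past IP stop is reasonable, since Protocol 1.2 allows that low drug levels may persist for several days, but that does not make four weeks on-therapy.

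**What to change.** In SAP 3.3.1, keep the all-period TEAE tables as the main comparison and call them treatment emergent only, without 'on-therapy'. Add descriptive tables of TEAEs, severe TEAEs and serious TEAEs by onset period, with participant-time in each period by arm:

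- (a) IP initiation to actual IP stop;
- (b) IP stop to 24 hours after;
- (c) remaining follow-up.

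Flag each event as starting before or after the first IV anesthetic given for SE. The 24-hour cut matches the end of continuous EEG, scheduled PK sampling and vasopressor recording.

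The SAP classifies events by onset date, and the documents do not say that onset clock time is captured. If only dates are available, state a same-day assignment rule before unblinding and report how many events it affects. On the other side of the flag, Protocol 5.2 has each anesthetic dose recorded separately until 120 hours after IP stop.

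The cost is a wording change and three repeated tables. Counts per table will be small. Because IP stops at anesthesia, period (a) is shorter in treatment failures and its length depends on outcome. Participant-time makes this visible but does not remove the selection. The SAP should therefore call these tables supportive, to be read only beside the all-period table.

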3.3.2 Vital Signs

Vital signs include weight (kg), height (cm), temperature (°C), systolic blood pressure (mmHg), diastolic blood pressure (mmHg), pulse rate (bpm), respiration rate (breaths per minute), and oxygen saturation (%). Descriptive statistics for vital signs and changes from baseline values at each time point will be provided for each parameter.

All vital signs data will be presented in the participant data listings.

3.3.3 Laboratory Evaluations

All laboratory parameters will be presented in Standard International (SI) units. Only scheduled lab parameters will be included in the lab summaries.

Laboratory data collected in this study include serum chemistry and hematology values, urinalysis results, pregnancy results, and drug of abuse results. The baseline laboratory value is defined as the last value observed prior to IP initiation. Any values collected after IP initiation are regarded as post-baseline. Change from baseline will be calculated as the post-baseline value minus the baseline value. Only the numeric part in laboratory values that contain non-numeric qualifiers, such as less than (<) a certain value or greater than (>) a certain value, will be used in the summary statistics.

Quantitative results (including actual value and change from baseline) will be summarized using descriptive statistics by baseline and post-baseline visit for each laboratory test based on the Safety Population. Shift tables cross-tabulating the baseline and post-baseline classifications (below [L], Normal [N], or above [H] the reference range), by visit, will be provided.

All laboratory data will be included in the listing, including whether the value was below (L), within (N), or above (H) the normal reference range (some urinalysis labs are assigned only normal and abnormal classifications).

Pregnancy results performed on selected participants will be listed.

Screening results for drugs of abuse, including alcohol, will be listed separately.

All blood gas results, including FiO₂, PaO₂, and arterial pH, if available will be listed.

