4.5.2 Participant Withdrawal Criteria

The Sponsor is not providing formal thresholds to discontinue a participant from the study. The Sponsor encourages the investigator to continuously assess any potential risks and benefits of participation during the entire study. The investigator should not hesitate to discontinue a participant from the clinical study if, according to the investigator's clinical judgment, the risks exceed any potential benefits. Reference examples below.

1. If the participant experiences worsening and persistent ventilatory depression despite routine clinical interventions (e.g., jaw thrust, chin lift or oxygen supplementation) that, in the judgment of the investigator, can be improved upon by discontinuation of the IP, the investigator may choose to discontinue such participant from the study. If positive ventilatory support is initiated and the participant is stable as per the investigator's clinical judgment, IP may be continued.
2. ECG evidence of QT prolongation (QTcF >500 msec, or an increase of QTcF >60 msec above baseline to a value >480 msec on the 12 lead ECG, confirmed on a repeat 12-lead ECG taken after resting at least 5 minutes in a supine or semi recumbent position after the original finding of prolonged QTcF).
3. Kidney function impairment such that eGFR ≤ 44 mL/min/1.73m² and participant is not starting dialysis.

4. Any other adverse event or safety issue (e.g., severe persistent hypotension/hypertension or tachycardia/bradycardia) that suggests it is not in the participant's best interest to continue to receive IP.
5. Rash that is clinically significant and considered to be related to the IP (e.g., morbilliform, urticarial, papular).
6. Participant experiences an SAE considered to be related to the IP.

Decisions to discontinue from the study will be made by the investigator. If feasible, the reason for discontinuation should be discussed with the Medical Monitor prior to the participant's discontinuation unless due to the progression to anesthesia for seizure suppression.

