6.2.4 Investigational Product Infusion Precautions

Throughout the study, heart rate and rhythm, blood pressure, and oxygen saturation are monitored. Investigational product may be temporarily or permanently discontinued, if clinically indicated, for treatment of persistent hypotension (sustained systolic blood pressure <90 mmHg), cardiac arrhythmia or oxygen desaturation.

Due to Captisol® presence in the IV formulation of the IP, renal function will be monitored throughout the study. In addition to standard and accepted biomarkers of renal function (i.e., creatinine clearance and estimated glomerular filtration ratio [eGFR]), urinary exploratory biomarkers of renal function (N-acetyl-β-D-glucosaminidase [NAG], β2-microglobulin, and creatinine) will be monitored throughout the study and reviewed by the DMC.

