2. STATISTICAL CONSIDERATIONS

2.1 General Considerations

- The treatment groups will be coded as “Ganaxolone” and “Placebo,” and all summary tables will be provided by treatment group and overall. When applicable, treatment in open-label phase will be coded as “Openlabel Ganaxolone”.
- In general, descriptive statistics (n, mean standard deviation [SD], median, 25th and 75th percentiles, minimum, and maximum) will be summarized by treatment group for continuous variables. Means and medians will be presented with one more decimal place than the precision of the data. Standard deviations will be presented with two more decimal

places than the precision of the data. Minimums and maximums will be presented with the same precision as the original data.

- Count and percentage of participants in each category will be provided for categorical variables. Unless stated otherwise, percentages are based on the number of participants in the treatment group of the analysis set. Percentages will be presented with one decimal place (xx.x), with the exception of 100%, which will be displayed without any decimal places, and the exception of 0%, which will not be displayed.
- All listings will be listed by treatment group, participant, test parameter, and time point (if applicable).
- Scheduled assessments will be included in summaries. Unscheduled assessments will only be included in the display sections that report abnormal laboratory results, vital signs, or ECG values. Data from all assessments (scheduled or unscheduled), will be included in the listings.
- Unless stated otherwise, baseline is defined as the last non-missing value prior to the first dose of study drug administration.
- P-values will be reported to 3 decimal places, with values less than 0.001 displayed as “<0.001.”
- All outputs should have the following header at the upper left margin:

Marinus Pharmaceuticals, Inc.
Study 1042-SE-3003

And the following header (right justified) at the upper right margin:

Page n of N

Tables/appendices/listing should be internally paginated (i.e., page numbers should appear sequentially within each table). All outputs should have SAS program name, source listing, and execution date and time included in the footnotes.

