2.3 Time Windows for Analyses

For by-visit safety or efficacy summaries, only scheduled visits will be analyzed. Data collected at unscheduled visits will be provided in listings.

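### SAP 2.1 sends unscheduled abnormal values to displays that SAP 3.3.2–3.3.4 do not specify, and no table counts participants by arm at the protocol's QTcF, eGFR or SBP levels

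*SAP*

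**What the plan says.** SAP 2.1 sets the general rule: "Unscheduled assessments will only be included in the display sections that report abnormal laboratory results, vital signs, or ECG values". It adds that "Data from all assessments (scheduled or unscheduled), will be included in the listings".

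SAP 2.3 covers visit-based output: "For by-visit safety or efficacy summaries, only scheduled visits will be analyzed", and "Data collected at unscheduled visits will be provided in listings".

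The safety sections then specify the following.

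- **Vital signs (SAP 3.3.2):** descriptive statistics for values and changes at each time point, plus listings.
- **Laboratory (SAP 3.3.3):** descriptive statistics by visit, and one table of abnormality: "Shift tables cross-tabulating the baseline and post-baseline classifications (below [L], Normal [N], or above [H] the reference range), by visit, will be provided". The section's overall restriction is "Only scheduled lab parameters will be included in the lab summaries". All values are listed with range flags.
- **ECG (SAP 3.3.4):** descriptive statistics by time point, and counts of participants by investigator interpretation. The section does not say whether unscheduled tracings count.

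The protocol names its own levels of concern. Section 4.5.2 gives "ECG evidence of QT prolongation (QTcF >500 msec, or an increase of QTcF >60 msec above baseline to a value >480 msec", to be confirmed on a repeat tracing, and eGFR of 44 mL/min/1.73m² or less in a participant who is not starting dialysis. Section 6.2.4 gives "persistent hypotension (sustained systolic blood pressure <90 mmHg". Section 4.5.2 says that it sets no formal discontinuation thresholds and offers its list as examples. The blood-pressure level is an infusion precaution.

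**The concern.** The general rule points to displays that the detailed sections do not set up for unscheduled data, and for laboratory values the detailed section excludes those data. A programmer following SAP 3.3.3 would drop values that SAP 2.1 says to show.

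This matters because the most extreme values in this population are often unscheduled. Laboratory samples are taken for an SAE or on clinical judgment. Vital signs and ECGs may be repeated at any time, and the protocol's QTcF example itself requires a repeat ECG. Safety is part of the primary objective. Hypotension was a TEAE in 4 of 17 phase 2 participants (23.5%), and renal function is monitored because of the Captisol content. A reader comparing arms would want to know how many participants reached these levels, and no planned table says so.

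**Working it through.** No sample size, alpha or power is involved, so the check sets the sections side by side and reads the assessment schedule.

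**1. Displays specified for abnormal values**

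| Domain | Display that reports abnormality | Unscheduled values included? | Uses the protocol's level? |
|---|---|---|---|
| Laboratory (3.3.3) | Low/normal/high shift table by visit | No (2.3 and 3.3.3) | No: laboratory reference range |
| Vital signs (3.3.2) | None beyond descriptive statistics | No such display | No |
| ECG (3.3.4) | Interpretation counts | Not stated; excluded by 2.3 if by visit | No QTcF categories |

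Apart from listings, the number of displays stated in SAP 3.3.2–3.3.4 to include unscheduled values is 0. The number built on the QTcF, eGFR or SBP levels is 0.

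**2. How direct the conflict is**

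- *Laboratory:* direct. The only abnormality table is a summary by visit, and 3.3.3 limits summaries to scheduled values.
- *Vital signs:* the destination named in 2.1 does not exist in 3.3.2.
- *ECG:* ambiguous. If the interpretation count is by visit, 2.3 excludes unscheduled tracings; if it is per participant overall, 2.1 would admit them.

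**3. What the schedule leaves to unscheduled sampling** (Protocol Table 1 and footnotes)

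- *Chemistry:* predose, or within 2 h after initiation if predose was not possible; then at IP discontinuation, 24 h later, at discharge and at weekly follow-up. With a completed taper, discontinuation is nominally at 48 h. The interval without a planned draw is 48 − 0 = 48 h, or 48 − 2 = 46 h after a late first sample. A renal change first found during infusion would usually come from an unscheduled or SAE-triggered sample.
- *Safety ECG:* predose and 2 h, then IP discontinuation. The gap is 48 − 2 = 46 h. The repeat tracing needed to confirm a QTcF finding is outside this schedule.
- *Vital signs:* about 1, 2, 6, 10, 24 and 36 h, with gaps of up to 24 − 10 = 14 h. Scheduled readings alone cannot establish that low pressure was sustained between visits.

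**4. Where a breach can appear**

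- *At a scheduled visit:* SAP 2.1 defines descriptive statistics to include the minimum and maximum, so an extreme value bounds the printed range. A laboratory value outside its reference range enters the shift table, and an abnormal ECG enters the interpretation counts. None of these gives the number of participants at the protocol's level.
- *At an unscheduled assessment:* in the listing and, if the investigator considers it clinically significant, as an AE (Protocol 7.2.3.4, 7.2.3.5, 8.1.5) and so in the TEAE tables of SAP 3.3.1.

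**5. Why an eGFR count is informative.** Known or suspected eGFR of 44 or below is excluded at entry (Protocol 4.2, criterion 9), so a later value at that level would usually be new.

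**The case against.** The strongest reply is that the adverse-event route already covers what matters. Clinically significant vital-sign deviations are to be recorded as AEs, and significant laboratory and ECG changes can be. TEAEs are tabulated by arm, severity, seriousness and drug discontinuation, whether or not the measurement was scheduled. A sample drawn for an SAE accompanies an event already in the serious TEAE tables. The phase 2 hypotension figure is itself a TEAE count. The DMC sees accumulating safety data, including renal biomarkers, and table templates are filed outside the SAP.

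Much of this stands, and it rules out several stronger readings that a reader might infer.

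- *That breaches stay out of every table.* They do not: the minimum and maximum, the shift table, the ECG interpretation counts and the TEAE tables can each carry one.
- *That the SAP plans only means, or no display of abnormality at all.* Section 2.1 and the laboratory and ECG tables say otherwise.
- *That hypotension soon after the bolus would be lost because the first scheduled reading is at about 60 minutes.* Blood pressure is monitored throughout, and an AE with onset from IP initiation is treatment-emergent.
- *That vasopressor use goes untabulated.* Continuous infusions are recorded on the medication form, and SAP 3.1.5 summarises concomitant medications by arm.
- *That the levels are formal thresholds.* Protocol 4.5.2 says they are not.

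What the reply does not remove: the AE route depends on investigator judgment and coding and counts preferred terms, not participants reaching a level. Listings give no comparison by arm. DMC review protects participants during conduct but does not supply the final tables. Unseen templates cannot reconcile 2.1 with 3.3.3.

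**Conclusion.** The point holds as a gap in safety reporting and an internal inconsistency. For laboratory values, SAP 2.1 and 3.3.3 conflict; for vital signs, the display that 2.1 relies on is not specified; for ECGs, the handling of unscheduled tracings is left open. No table counts participants by arm at the protocol's QTcF, eGFR or SBP levels, and unscheduled values reach tabulated output only through the AE route.

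The size cannot be put as a number of participants, because the documents do not say how many unscheduled values exist. The structural size is 0 specified displays with unscheduled values, 0 with the protocol's levels, and about 46 to 48 hours of infusion without planned chemistry. That interval assumes a completed taper; earlier discontinuation shortens it. The conclusion rests on the SAP text alone. Efficacy inference is unaffected.

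**What to change.** 1. **Reconcile the rules.** Replace the scheduled-only sentence in SAP 3.3.3 with: *By-visit summaries use scheduled values; worst-value and threshold tables use all post-IP values.* Align 2.1 and 2.3 with it, and state in 3.3.4 whether unscheduled tracings enter the interpretation counts.
2. **Add laboratory shift tables by arm** from baseline to worst post-baseline value. Include a missing-baseline row, since 3.3.3 treats a first sample drawn after IP initiation as post-baseline.
3. **Add counts by arm** of participants with any post-IP SBP <90 mmHg; QTcF >500 msec, or a rise >60 msec to a value >480 msec; and eGFR of 44 or less. Label these as any-value counts, because they are broader than the protocol's wording.
4. **Where data allow, show separately** those who meet the protocol's qualifiers: sustained low pressure, QTcF confirmed on a repeat ECG, and eGFR at that level without starting dialysis. Give the number with an available eGFR as the denominator, since eGFR is collected only if available.

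The cost is SAP wording and a few tables from data already collected; no clinical rule changes. The drawback is that sicker participants are sampled more often and so have more chances to reach a level. Presenting these tables beside the by-visit summaries lets the reader judge that.
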